5.9. Analysis of Pharmacokinetic Data

The concentrations of REGN10933 and REGN10987 in serum over time will be summarized descriptively for each of the treatment groups. No formal statistical hypothesis testing will be performed.

5.10. Analysis of Immunogenicity Data

5.10.1. Analysis of ADA Data

The immunogenicity variables described in Section 4.8 will be summarized using descriptive statistics. Immunogenicity will be characterized per drug molecule by ADA status, ADA category, and maximum titer observed in subjects in the ADA analysis sets.

The ADA status of each subject may be classified as one of the following:

- Positive
- Pre-existing – If the baseline sample is positive and all post baseline ADA titers are reported as less than 9-fold the baseline titer value
- Negative – If all samples are found to be negative in the ADA assay.

The ADA category of each positive subject is classified as:

- Treatment-boosted – A positive result at baseline in the ADA assay with at least one post baseline titer result \geq 9-fold the baseline titer value

- Treatment-emergent – A negative result or missing result at baseline with at least one positive post baseline result in the ADA assay. Subjects that are treatment-emergent will be further categorized as follows:
 - Persistent – A positive result in the ADA assay detected in at least 2 consecutive post baseline samples separated by at least a 16-week post baseline period (based on nominal sampling time), with no ADA-negative results in-between, regardless of any missing samples
 - Transient – Not persistent or indeterminate, regardless of any missing samples
 - Indeterminate – A positive result in the ADA assay at the last collection time point only, regardless of any missing samples.

The maximum titer category of each subject is classified as:

- Low (titer <1,000)
- Moderate (1,000 ≤ titer ≤ 10,000)
- High (titer >10,000)

The following will be summarized by treatment group and ADA titer level:

- Number (n) and percent (%) of ADA-negative subjects
- Number (n) and percent (%) of pre-existing subjects
- Number (n) and percent (%) of treatment-emergent ADA positive subjects
 - Number (n) and percent (%) of persistent treatment-emergent ADA positive subjects
 - Number (n) and percent (%) of indeterminate treatment-emergent ADA positive subjects
 - Number (n) and percent (%) of transient treatment-emergent ADA positive subjects
- Number (n) and percent (%) of treatment-boosted ADA positive subjects

Listing of all ADA titer levels will be provided for subjects with pre-existing, treatment-emergent and treatment-boosted ADA response.

5.10.2. Analysis of NAb Data

The absolute occurrence (n) and percent of subjects (%) with NAb status in the NAb analysis sets will be provided by treatment groups. The NAb status is categorized as follows:

- Negative: Samples tested negative in the ADA assays, or samples positive in the ADA assays but tested negative in the NAb assays, or ADA-positive results without NAb analysis results.
- Positive: Samples tested positive in the NAb assays.

5.10.3. Association of Immunogenicity with Exposure, Safety and Efficacy

5.10.3.1. Immunogenicity and Exposure

Potential association between immunogenicity and systemic exposure to REGN10933 and REGN10987 will be explored by treatment groups. Plots of individual REGN10933 and REGN10987 concentration time profiles may be provided to examine the potential impact of ADA category, maximum titer category and NAb status on these profiles.

5.10.3.2. Immunogenicity and Safety and Exposure

Potential association between immunogenicity variables and safety may be explored with a primary focus on the following safety events during the TEAE period:

- Injection site reaction (serious or severe and lasting 24 hours or longer)
- Infusion reactions
- Hypersensitivity (SMQ: Hypersensitivity [Narrow])
- Anaphylaxis (SMQ: Anaphylaxis [Narrow])

Potential association between immunogenicity variables and efficacy endpoints may be explored (e.g., scatter plot or spaghetti plot).

The safety and efficacy analyses mentioned above will be conducted using the following categories:

- ADA positive
 - Treatment-emergent
 - Treatment-boosted
- Maximum post-baseline titer category
- NAb positive

6. DATA CONVENTIONS

The following analysis conventions will be used in the statistical analysis.

6.1. Definition of Baseline

Unless otherwise specified, the baseline assessment for all measurements will be the latest available valid measurement taken prior to the administration of the first dose of Moderna mRNA-1273 vaccine or REGN10933+REGN10987 (as applicable and whichever occurs first).

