8.5. Method of Enrollment and Treatment Assignment

Site-managed assignment. At screening, eligible subjects will be assigned to an enrollment wave. The enrollment waves are intended to avoid or minimize the potential for unused doses of Moderna mRNA-1273 COVID-19 vaccine (refer to Section 3.2.1 for additional rationale). Every effort should be made by sites to avoid unused doses of vaccine.

Sites will manage the placement of subjects into each wave. Every effort should be made by the site to ensure balance of age (<65 years and \geq 65 years) within each of the enrollment waves.

Randomization. At baseline (day 1), subjects will be randomized to the corresponding study arms in each wave as described in [Table 2](#).

Randomization will be performed according to a computer-generated randomization scheme provided by an interactive web response system (IWRS) to a designated study pharmacist or a qualified designee.

Randomization will be stratified by age (<65 years versus \geq 65 years).

Table 2: Study Treatment Assignment

Study Arm	Randomization Ratio	Targeted Enrollment	Co-administered REGN10933+REGN10987 Combination Therapy	Moderna mRNA-1273 Vaccine*
Enrollment Wave 1				
1	2	30	1200 mg (600 mg of each mAb) IV on day 1	On day 15 and day 43
2	2	30	300 mg (150 mg of each mAb) IV on day 1	On day 15 and day 43
3	2	30	150 mg (75 mg of each mAb) IV on day 1	On day 15 and day 43
6a	1	15	None	On day 15 and day 43
Enrollment Wave 2				
4	2	30	1200 mg (600 mg of each mAb) SC on day 1	On day 1 and day 29
5	2	30	600 mg (300 mg of each mAb) SC on day 1	On day 1 and day 29
6b	1	15	None	On day 1 and day 29
Enrollment Wave 3				
7	15	30	48 mg (24 mg of each mAb) IV on day 1	On day 15 and day 43
8	15	30	12 mg (6 mg of each mAb) IV on day 1	On day 15 and day 43
6c	4	8	None	On day 15 and day 43
Enrollment Wave 4				
9	15	30	1200 mg (600 mg of each mAb) IV on day 7	On day 1 and day 29
6d	4	8	None	On day 1 and day 29

*Moderna mRNA-1273 vaccine will be administered as described on the EUA Fact Sheet ([Moderna COVID-19 Vaccine \[HCP Fact Sheet\], 2022](#)).

mAb=monoclonal antibody; SC=subcutaneous; IV=intravenous.

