Serum for SARS-CoV2 neutralization ⁸			X			X			X	X	X	X	X	X	X	X	X
Serum for serology characterization ⁸		X				X			X	X	X	X	X	X	X	X	X
Whole blood for PBMCs ⁸		X			X			X	X	X	X	X	X	X	X	X	X
Serum for exploratory research		X			X			X	X	X	X	X	X	X	X	X	X
Plasma for exploratory research		X			X			X	X	X	X	X	X	X	X	X	X
Safety																	
Vital signs ⁹	X	X ⁹		X ⁹	X ⁹		X ⁹		X ⁹								
Adverse events ¹²	X	X	X	X	X	X	X	X	X	X	X	X	X	X	X	X	
Concomitant medications	X	X	X	X	X	X	X	X	X	X	X	X	X	X	X	X	
Targeted physical examination	X																
Laboratory Testing (Central Lab)																	
Hematology			X			X				X		X	X			X	X
Blood Chemistry		X			X			X			X	X	X			X	X
Urinalysis			X														X
Drug concentrations and Immunogenicity																	
Drug concentration (PK) sample ¹⁰						X ¹⁰			X ¹⁰	X	X	X	X	X			
Immunogenicity (ADA) sample ¹¹						X ¹¹							X				
Pharmacogenomics (Optional)																	
Whole Blood for DNA			X ²														
Vaccine Booster Sub-Study (Optional)¹⁴																	

Visit Period	Screening/Baseline						Vaccine Response Assessment						Follow-Up			Unscheduled Visit	ET
	-21 to 1						7			15	29 ¹	43	57	169	253	366	
	Study Day	Screening	Pre-dose	Dose ¹	Post-Dose	Pre-dose	Dose ¹	Post-Dose	14	28	42	56	168	252	365		
Days After the First Vaccine Dose									±2	-1 to +3	±2	±2	±7	±14	±14		
Window (day)																	
Informed consent for vaccine booster sub-study ²						Refer to Table 6 .											
Sample collection and assessments																	

Table 6: Schedule of Events for the Moderna mRNA-1273 Vaccine Booster Sub-Study

Visit	Vaccine Booster Administration			Post-Booster Follow-Up
	Pre-Dose	Dose ¹	Post-Dose	
Visit Window	≥5 months after the second dose of the vaccine (primary series), and >35 days before end of the main study			28 days ±7 days after the vaccine booster
Informed consent for the booster sub-study ²	X			
Moderna mRNA-1273 vaccine booster shot		X		
Pregnancy test (WOCBP) ³	X			
SARS-CoV-2 rapid (local/POC) RT-PCR ⁴		X ⁴		X ⁴
Adverse events ¹²	X	X	X	X
Drug concentration (PK) sample ¹⁰	X			X
Serum for exploratory research	X			X
Plasma for exploratory research	X			X
Whole blood for PBMCs ⁸	X			X

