Study arms 6a, 6b, 6c, and 6d (receiving no study drug): No blood for assessment of drug concentration in serum will be collected.

11. The window for pre-dose ADA sample collection should be as close to administration of study drug as is reasonable. Actual dosing time and ADA sample collection times will be recorded.
- Study arms 6a, 6b, 6c, and 6d (receiving no study drug):** No blood for ADA assessment will be collected.
12. Adverse events will be continuously monitored as described in Section 10.1.1.
13. **For Arms 1, 2, 3, 6a, 6c, 7 and 8:** For subjects receiving their COVID-19 vaccine booster as part of the sub-study, the vaccine booster may be administered at any time from 5 months after their second vaccine dose until study day 345. The *actual date* the subject received their second vaccine dose should be used (as opposed to using study day 43) to determine when the booster window should begin.
14. **For Arms 4, 5, 6b, 6d, and 9:** For subjects receiving their COVID-19 booster as part of the sub-study, the vaccine booster may be administered at any time from 5 months after their second vaccine dose until study day 331. The *actual date* the subject received their second vaccine dose should be used (as opposed to using study day 29) to determine when the booster window should begin.

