2. INVESTIGATION PLAN

2.1. Study Design and Randomization

This study is a phase 2, randomized, open-label, parallel group study in healthy adult volunteers to assess the immunogenicity, safety, and tolerability of Moderna mRNA-1273 vaccine when administered with REGN10933+REGN10987.

At screening, eligible subjects were to be assigned to an enrollment wave. The enrollment waves were intended to avoid or minimize the potential for unused doses of Moderna mRNA-1273 COVID-19 vaccine (Protocol Section 3.2.1 for additional rationale). Every effort was made by sites to avoid unused doses of vaccine.

Every effort was made by the site to ensure balance of age (<65 years and \geq 65 years) within each of the enrollment waves. At baseline (day 1), subjects were to be randomized to the corresponding study arms in each wave as described in [Table 1](#).

Randomization was performed according to a computer-generated randomization scheme provided by an interactive web response system (IWRS) to a designated study pharmacist or a qualified designee.

Randomization was stratified by age (<65 years versus \geq 65 years).

Table 1: Study Treatment Assignment

Study Arm	Randomization Ratio	Targeted Enrollment	Co-administered REGN10933+REGN10987 Combination Therapy	Moderna mRNA-1273 Vaccine*
Enrollment Wave 1				
1	2	30	1200 mg (600 mg of each mAb) IV on day 1	On day 15 and day 43
2	2	30	300 mg (150 mg of each mAb) IV on day 1	On day 15 and day 43
3	2	30	150 mg (75 mg of each mAb) IV on day 1	On day 15 and day 43
6a	1	15	None	On day 15 and day 43
Enrollment Wave 2				
4	2	30	1200 mg (600 mg of each mAb) SC on day 1	On day 1 and day 29
5	2	30	600 mg (300 mg of each mAb) SC on day 1	On day 1 and day 29
6b	1	15	None	On day 1 and day 29
Enrollment Wave 3				
7	15	30	48 mg (24 mg of each mAb) IV on day 1	On day 15 and day 43
8	15	30	12 mg (6 mg of each mAb) IV on day 1	On day 15 and day 43
6c	4	8	None	On day 15 and day 43
Enrollment Wave 4				
9	15	30	1200 mg (600 mg of each mAb) IV on day 7	On day 1 and day 29

6d	4	8	None	On day 1 and day 29
----	---	---	------	---------------------

*Moderna mRNA-1273 vaccine will be administered as described on the US FDA EUA HCP Fact Sheet, 2021)
mAb=monoclonal antibody; SC=subcutaneous; IV=intravenous.

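### As written, SAP 6.1 leaves arm 9 without an ADA baseline, so reactivity present before any study drug is classed as treatment-emergent

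*SAP*

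**What the plan says.** **General rule.** SAP 6.1 covers every measurement for which the SAP gives no other rule, and fixes baseline at the last valid value "prior to the administration of the first dose of Moderna mRNA-1273 vaccine or REGN10933+REGN10987 (as applicable and whichever occurs first"). The one different baseline in the SAP is in section 5.7, for efficacy variables. SAP 4.8 and 5.10.1, which cover ADA, define none.

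**Arm 9 dosing.** Protocol 8.5, Table 2 gives study drug as "1200 mg (600 mg of each mAb) IV on day 7". SAP Table 1 gives the arm 9 vaccine as "On day 1 and day 29". Arm 9 is the only arm in which vaccine comes before study drug.

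**Arm 9 ADA sampling.** Footnote 11 to the schedules says: "The window for pre-dose ADA sample collection should be as close to administration of study drug as is reasonable". In Protocol Table 5 the first mark in the ADA row stands at the day-7 pre-dose position, and there is none on day 1.

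**Classification.** SAP 5.10.1 defines treatment-emergent ADA as "A negative result or missing result at baseline with at least one positive post baseline result in the ADA assay". Persistent means positive in "at least 2 consecutive post baseline samples separated by at least a 16-week post baseline period". Pre-existing and treatment-boosted both need a positive baseline sample.

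**The concern.** The general rule fits the other drug arms. In arms 1 to 5, 7 and 8 study drug is the first product given, so the sample before drug is also the sample before everything. In arm 9 the two events are six days apart and the only pre-drug ADA sample falls after the first vaccine dose. A rule tied to whichever product comes first therefore skips the sample that should serve as the ADA baseline.

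Immunogenicity of REGN10933 and REGN10987 is a secondary objective and endpoint, and SAP 5.10.1 tabulates ADA categories by treatment group. An error confined to arm 9 would be differential across arms. It would move pre-drug reactivity into the category that signals a response to the drug, in the one arm where a reader might look for an effect of prior vaccination on that response. The same categories, and the maximum post-baseline titer, are used in the optional displays of SAP 5.10.3.

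**Working it through.** The plan states no figure to reproduce here. The check applies the SAP rules to arm 9.

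**Inputs**
- Vaccine on day 1, study drug on day 7 (Protocol Table 2, SAP Table 1).
- First ADA sample on day 7, pre-drug (Protocol Table 5, footnote 11).
- Second ADA sample on day 169. This is inferred from the column position of the second mark in the Protocol Table 5 ADA row. The table is damaged in the text version, and SAP Table 4 there shows only the day-7 mark.
- Category definitions from SAP 5.10.1.
- 30 planned subjects in arm 9.

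**Step 1: baseline status.** Under SAP 6.1, baseline must precede the day-1 vaccine. No ADA sample is scheduled before it, so baseline is missing and day 7 is post-baseline.

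**Step 2: persistence interval.** 169 − 7 = 162 days = 23.1 weeks, above 16 weeks (112 days). Were the second sample at day 57 instead, 57 − 7 = 50 days = 7.1 weeks, and the persistence criterion would not be met.

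**Step 3: classification by pattern, with the second sample at day 169**

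| Day 7 (pre-drug) | Day 169 | SAP 6.1 as written | Baseline = last sample before drug |
|---|---|---|---|
| negative | negative | negative | negative |
| negative | positive | treatment-emergent, indeterminate | treatment-emergent, indeterminate |
| positive | negative | treatment-emergent, transient | pre-existing |
| positive | positive, below 9-fold | treatment-emergent, persistent | pre-existing |
| positive | at least 9-fold | treatment-emergent, persistent | treatment-boosted |

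The label changes in exactly the three patterns with a positive pre-drug sample. On this schedule arm 9 has one post-drug sample, so a persistent result there could arise only when the pre-drug sample is positive.

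**Step 4: size.** The documents give no prevalence *p* of pre-drug reactivity, so *p* is an assumption, per antibody. Expected number = 30 × *p*; chance of at least one = 1 − (1 − *p*)^30.

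| Assumed *p* | Expected of 30 | Chance of at least one |
|---|---|---|
| 1% | 0.3 | 26% |
| 2% | 0.6 | 45% |
| 5% | 1.5 | 79% |
| 10% | 3.0 | 96% |

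If all 30 are in the ADA analysis set, each case moves the arm 9 percentage by 1/30 = 3.3 points.

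**The case against.** The strongest reply is that the documents already think of ADA relative to study drug. SAP 3.7 admits subjects to the ADA sets on results after the first dose of the respective study drug, and Protocol 11.3.5 does the same. Footnote 11 ties the pre-dose sample to study drug. Protocol 11.4.9 makes treatment-emergence depend on a positive result after the first dose, and SAP 1.2.5 lists no ADA departure from the protocol. A programmer might well use day 7 as baseline without being told.

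This shows that the literal result is unintended, but it does not remove it. The analysis-set rules decide who is counted, not which sample is baseline. Protocol 11.4.9 refers to baseline without saying which sample it is. Even if its first dose means study drug, that wording alone rescues only the subject who is positive on day 7 and negative later. One who is positive at both samples, with baseline still missing, would remain treatment-emergent. The SAP trigger is in any case post-baseline, not post-drug.

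Two further replies stand. SAP 5.10.1 requires a listing of ADA titers for subjects in the pre-existing, treatment-emergent and boosted categories, so a positive day-7 result would be visible to a careful reader. The safety and efficacy associations and the exposure plots in SAP 5.10.3 are worded as things that may be done, so carry-over into them is possible but not certain.

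**Conclusion.** The point holds as a wording error in the SAP: a stated rule gives the wrong ADA category in arm 9. All 30 planned subjects lose their baseline under the literal rule, but only those reactive before drug are misclassified. That number is unknown and may be zero; 0.3 to 3 subjects follows solely from the assumed 1% to 10%.

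A reader might go further in three ways that the documents do not support:
- **False persistent ADA as an established consequence.** It depends on the day-169 placement, which is inferred. The treatment-emergent misclassification does not depend on it.
- **A spurious vaccine-priming signal.** No prevalence is given, the expected counts are small, and Protocol 11.1 plans only descriptive and exploratory analyses.
- **The same fault in NAb status and drug concentrations.** SAP 5.10.2 classifies NAb without comparison to baseline, and SAP 3.7 already uses post-dose NAb results. SAP 5.9 summarises concentrations over time with no baseline-dependent variable.

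The issue concerns one secondary endpoint in one of eight drug arms. It leaves the primary endpoint and the adverse-event counts untouched. It should be corrected because the correction is easy, not because it threatens the trial's main conclusions.

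**What to change.** Add to SAP 5.10.1, as an exception to 6.1: *For ADA, baseline is the last sample before the first dose of study drug, and post-baseline means after that dose.* In arm 9 this makes the day-7 pre-drug sample the baseline. In the other drug arms nothing changes, because the same sample is baseline under either rule. No baseline change is needed for NAb status or drug concentration.

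Keep the split into persistent, transient and indeterminate. Add a table footnote that arm 9 appears to have one scheduled post-drug ADA sample, so a treatment-emergent positive there can only be indeterminate. Confirm the day of that sample against the intact schedule before finalising the footnote.

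The cost is one sentence and one footnote in the SAP, with no new samples or visits.

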6.2. Data Handling Convention for Vaccine Response Variables

Values below the LLOQ will be set to half of LLOQ and values above the upper limit of quantification (ULOQ) will be set to the ULOQ. If two or more measurements correspond to the same visit, the lowest value will be used.

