11.4. Statistical Methods

For continuous variables, descriptive statistics will include the following information: the number of subjects reflected in the calculation (n), mean, standard deviation, Q1, median, Q3, minimum, and maximum. For categorical or ordinal data, frequencies and percentages will be displayed for each category.

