11.4.3. Analysis of Primary Vaccine Response Endpoint

The primary endpoint is the 50% inhibitory dilution (ID₅₀) titers of vaccine-induced neutralizing antibodies to SARS-CoV-2 pseudovirus, assessed on 56 days after the first dose of the vaccine (ie, the vaccine response assessment period). The 56-day time point corresponds to study day 71 for study arms 1, 2, 3, 7, 8, 6a, and 6c, and study day 57 for study arms 4, 5, 9, 6b, and 6d.

An analysis of covariance (ANCOVA) model with treatment group as a fixed effect and age as a covariate will be fit to the data as the primary analysis.

The least squares mean estimates for the endpoint will be presented for each treatment group, as well as for the differences between treatment groups. Associated 95% confidence intervals will also be reported for each treatment group and for between-group comparisons.

Data will be fitted in the log scale, and final outputs will be reported in geometric means and differences of the geometric means.

Accompanying descriptive analyses will also be provided. The analyses will be conducted based on the observed data with no imputation for missing data. Values below the limit of quantification (LOQ) will be set to half of LOQ.

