1.2.6. Revision History for SAP Amendments

The revised SAP (version 2) is based on Protocol Amendment 5 dated January 28th 2022.

Summary of Changes from Version 1 to Version 2	
Change and Rationale for Change	Sections changed
Edits and additions, due to protocol amendment and for added clarity.	Section 1
Secondary and exploratory objectives and endpoint wording updated to match changes in protocol amendment	Section 1.2.2, 1.2.3, 1.2.4 Section 4.5.2 Section 4.5.3
Clarify timeframe for criteria 7 of the Per Protocol Set	Section 3.1
Vaccine Booster Analysis Set is defined	Section 3.5
Clarify that the pharmacokinetics analysis sets	Section 3.6

are defined for each study drug separately	
Clarify immunogenicity analysis sets and analysis of immunogenicity data	Section 3.7 Section 5.10.1, 5.10.2
Add clarification that medications reporting to include standardized medication name	Section 4.3
Safety periods updated to match protocol amendment and reflect optional vaccine booster dose	Section 4.6.1
Added tabulation of subjects who receive vaccine booster dose along with time from completion of primary series of vaccine	Section 5.6
In alignment to other studies within the REGEN-COV program, handling rule for values above the upper limit of quantification (ULOQ) to be set to the ULOQ	Section 5.7 Section 6.2
Noted an exploratory analysis that will be performed with data from a second neutralization assay and summarized in a separate report	Section 5.7.3
Addition of analyses for vaccine booster analysis set subjects	Section 5.7.6
Removal of text referencing noncompartmental analysis due to sampling schedule	Section 5.9
Schedule of events updated to reflect protocol amendment	Section 11.1

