5. STATISTICAL METHODS

For continuous variables, descriptive statistics will include the following: the number of subjects reflected in the calculation (n), mean, median, standard deviation, minimum, and maximum. For categorical or ordinal data, frequencies and percentages will be displayed for each category.

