5.7.1. Analysis of Primary Vaccine Response Variable

The primary endpoint is the 50% inhibitory dilution (ID_{50}) neutralizing antibody titers of vaccine-induced neutralizing antibodies to SARS-CoV-2, assessed on 56 days after the first dose of the vaccine. The 56-day time point corresponds to study day 71 for study arms 1, 2, 3, 7, 8, 6a, and 6c, and study day 57 for study arms 4, 5, 9, 6b, and 6d. For all analyses, the vaccine alone arms (i.e. arms 6a, 6b, 6c and 6d) will be pooled in the analysis.

An analysis of covariance (ANCOVA) model with treatment group as a fixed effect and age as a continuous covariate will be run in order to perform the primary analysis for the PPS. The least squares mean estimates and associated 95% confidence interval for the endpoint will be reported for each treatment group, as well as for the relative differences between each combination of Moderna mRNA-1273 vaccine and REGN10933+REGN10987 arm (i.e. arms 1 - 5, and 7 - 9) and the pooled vaccine alone group.

Data may be fitted in the log 2 scale, and final outputs of geometric means and relative differences of the geometric mean ratio will be reported through the back-transformation.

Let $\hat{\mu}_A$, $\hat{\mu}_B$ denote the least squares mean estimates and $\hat{\sigma}_A^2$, $\hat{\sigma}_B^2$, $\hat{\sigma}_{AB}$ denote the associated estimated variances and covariance for the endpoint of interest of treatment groups A and B, respectively.

Geometric means and associated 95% confidence intervals for treatment groups A and B will be calculated as:

$$2^{\hat{\mu}_A}, (2^{\hat{\mu}_A - t_{df,\alpha} \times \hat{\sigma}_A}, 2^{\hat{\mu}_A + t_{df,\alpha} \times \hat{\sigma}_A}),$$

and

$$2^{\hat{\mu}_B}, (2^{\hat{\mu}_B - t_{df,\alpha} \times \hat{\sigma}_B}, 2^{\hat{\mu}_B + t_{df,\alpha} \times \hat{\sigma}_B}).$$

Relative difference of the geometric mean ratio and associated 95% confidence interval for treatment groups A and B will be calculated as:

$$(2^{\widehat{\mu}_A - \widehat{\mu}_B} - 1) \times 100\%, \left(2^{\frac{(\widehat{\mu}_A - \widehat{\mu}_B) - t_{df, \alpha} \times \sqrt{\widehat{\sigma}_A^2 - 2\widehat{\sigma}_{AB} + \widehat{\sigma}_B^2}}{2} - 1} \right) \times 100\%, \left(2^{\frac{(\widehat{\mu}_A - \widehat{\mu}_B) + t_{df, \alpha} \times \sqrt{\widehat{\sigma}_A^2 - 2\widehat{\sigma}_{AB} + \widehat{\sigma}_B^2}}{2} - 1} \right) \times 100\%.$$

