5.7.3. Analysis of Exploratory Vaccine Response Variables

Exploratory vaccine response variables will be analyzed in a similar manner as described for the secondary vaccine response variables.

Accompanying descriptive analyses will be provided to all (primary/secondary/exploratory) vaccine response variables.

The distribution of endpoint variables will be checked to ensure ANCOVA type analyses are appropriate. If such modeling is deemed not appropriate, only raw data descriptions will be provided.

On limited numbers of samples, an exploratory analysis will be performed with data from a second neutralization assay that will be summarized in a separate report.

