5.7.5. Supplementary and Subgroup Analyses

Supplementary analysis:

In order to assess the consistency of results due to concurrent randomization, analyses of the primary vaccine response variable may be performed separately within waves 1, 2 and within waves 3, 4, respectively.

Subgroup analysis:

The following subgroup analysis may be performed in Per Protocol Analysis Set in order to assess the consistency of results:

- age groups: <65 vs ≥ 65 (if applicable)
- gender: male vs female

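### Does setting titres above the ULOQ equal to the ULOQ, with no count of such values and no censored-data analysis, undermine the primary comparison?

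*SAP*

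**What the plan says.** SAP 6.2, repeated in 5.7, states that "values above the upper limit of quantification (ULOQ) will be set to the ULOQ"; values below the LLOQ become half the LLOQ. For the primary endpoint, SAP 5.7.1 specifies: "An analysis of covariance (ANCOVA) model with treatment group as a fixed effect and age as a continuous covariate will be run". The capped values enter that model as exact observations.

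The upper-limit rule arrived with SAP version 2. Section 1.2.6 gives its reason: "In alignment to other studies within the REGEN-COV program, handling rule for values above the upper limit of quantification (ULOQ"). Protocol 11.4.3 addresses the lower limit only: "Values below the limit of quantification (LOQ) will be set to half of LOQ".

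Three other places bear on whether capping would be noticed:

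- **Descriptive statistics.** SAP section 5 lists "the number of subjects reflected in the calculation (n), mean, median, standard deviation, minimum, and maximum". Protocol 11.4 lists n together with "mean, standard deviation, Q1, median, Q3, minimum, and maximum".
- **Model check.** SAP 5.7.3 has the distributions checked before ANCOVA is relied on, and adds: "If such modeling is deemed not appropriate, only raw data descriptions will be provided".
- **Supplementary analyses.** SAP 5.7.5 says "analyses of the primary vaccine response variable may be performed separately within waves 1, 2 and within waves 3, 4, respectively", and allows age and sex subgroups. Neither addresses values at the limit.

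**The concern.** A titre reported as above the ULOQ is right-censored: the true value is at least the limit. Replacing it with the limit lowers the group mean and shrinks the group variance. If the antibody reduces the vaccine response, the vaccine-alone group has the highest titres and is capped most. The difference between arms then shrinks and the log-scale confidence interval becomes too narrow.

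The first primary objective is the extent of the effect, and no hypothesis test is planned (Protocol 11.1), so the estimate and its interval are the result. The error would favour the clinical hypothesis in Protocol 3.1 that the antibody does not alter the vaccine's immunogenicity. The SAP's shorter descriptive list adds to the worry. A median sits at the cap only when about half of an arm is capped, and a maximum shows that the limit was reached but not how often.

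**Working it through.** **Inputs from the documents.** SD 0.30 on the log10 scale; 30 per antibody arm and 46 pooled controls (SAP 2.2); eight antibody arms, pooled control and continuous age in one model (SAP 5.7.1). Total 8 x 30 + 46 = 286. Residual degrees of freedom 286 - 9 - 1 = 276.

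**Assumptions.** The share of controls capped is varied, because no ULOQ is given. Log10 titres are normal. The true difference in the arm of interest is -0.20 log10, a reduction of 1 - 10^(-0.20) = 36.9%.

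**Step 1: the plan's own figure.** Half-width = 1.96 x 0.30 x sqrt(1/30 + 1/46) = 0.138. With t on 276 df it is 0.139. The SAP states 0.14, so it reproduces.

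**Step 2: expected estimate under capping.** For X normal with mean mu and SD s, capped at c, with z = (c - mu)/s:

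E[min(X, c)] = mu Phi(z) - s phi(z) + c (1 - Phi(z)).

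Set the control mean to 0. For 20% of controls capped, c = 0.8416 x 0.30 = 0.2525.

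- Control: -0.30 x 0.2800 + 0.2525 x 0.20 = -0.0335.
- Antibody arm: z = (0.2525 + 0.20)/0.30 = 1.508, giving -0.20 x 0.934 - 0.30 x 0.1279 + 0.2525 x 0.066 = -0.2086.
- Difference: -0.2086 + 0.0335 = -0.175, a shift of 0.025.

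**Step 3: range of capped shares.** The half-width uses the pooled SD of the capped data. Coverage is from simulating the nine-group plus age model. Where a range is shown, one end has only the arm of interest reduced and the other has all eight arms reduced.

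| Controls capped | Expected difference | Apparent reduction | Log10 half-width | Coverage of 95% CI |
|---|---|---|---|---|
| 0% | -0.200 | 36.9% | 0.139 | 95% |
| 5% | -0.195 | 36.1% | 0.133-0.137 | 94-96% |
| 20% | -0.175 | 33.2% | 0.117-0.128 | 91-94% |
| 30% | -0.160 | 30.8% | 0.106-0.122 | 86-91% |
| 40% | -0.144 | 28.1% | 0.096-0.114 | 75-85% |
| 50% | -0.126 | 25.1% | 0.084-0.105 | 57-73% |

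**Step 4: other true differences.** At 20% capped the shift is 0.021, 0.030 and 0.033 log10 for true differences of -0.15, -0.30 and -0.60. Each is under a quarter of the half-width (0.14/4 = 0.035). With no true difference the arms are capped equally and the shift is zero. At a true -0.10, coverage at 40% capped is 87-91%.

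**Step 5: smaller analysis set.** Under the SAP's conservative 50% exclusion (15 against 23), a true -0.20 with 40% capped gives coverage of 83-91%. The bias is unchanged but the interval is wider.

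**Step 6: what a censored model would add.** A censored-normal (Tobit) fit restores coverage to 93-95% on log-normal data. It leans on the tail it cannot see: with skewness of -1 or +1 and 40% capped, its mean estimate runs from -0.182 to -0.228 against a true -0.20. Its half-width at 40% capped is 0.142, against 0.096-0.114 for the ANCOVA.

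**The case for a change.** The strongest case for acting is that the absences are real, the bias runs in the convenient direction, and the remedy is cheap: one count by arm and one further model fit, with the primary analysis untouched. The model check in SAP 5.7.3 names no censoring criterion and falls back on description, so it yields no corrected ratio. The second neutralization assay mentioned there covers few samples and is reported separately. The analyses of VNT and WHO units, and those in the mFAS (SAP 5.7.4), fall under the same capping rule.

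All of that is accurate, and the arithmetic stands. What does not stand is the step from there to a defect.

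- The stated reason for the rule is alignment across the programme, not capping seen in this trial. The rule covers every vaccine response variable, binding antibody concentrations included, so its presence says nothing about day-56 neutralizing titres. The titre range of 256 to 1024 in Protocol 3.2.1.3 has no ULOQ to be set against.
- Detection is better than the SAP list alone suggests. Several arms sharing one maximum equal to the limit would show that capping occurred. SAP 1.2.5 lists the departures from the protocol's statistical section and does not include dropping the quartiles, so Q3 has not been openly withdrawn; it sits at the cap once about 25% of an arm is capped. Heavy piling at a single value is also what a distribution check would show.
- A Tobit fit triggered by a single value outside either limit would run in situations where Step 3 shows almost nothing to correct. Left-censoring below the LLOQ is a separate matter for which no problem has been shown.

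**Conclusion.** No change to the plan is needed. The SAP leaves a gap in reporting detail, but the documents do not show that the analysis as written gives a wrong answer. Up to about 20% of controls capped, the shift at a true -0.20 log10 is at most 0.025 log10 and coverage is 91-94%. Material loss begins at about 30% (86-91%) and is serious at 40-50% (75-85%, then 57-73%). It also requires a real reduction in titre; with equal arms there is no bias at any capped share.

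These figures rest on normal log10 titres, SD 0.30, full enrolment and an assumed effect. The capped share cannot be judged from the documents.

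The single-value rule is a fair trade-off. It is simple, consistent across the programme and fixed in advance of the final primary analysis, whereas a censored model brings its own dependence on tail shape. An analyst who saw several arms with the same maximum would state the ULOQ and give the number at the limit beside the descriptive statistics, and would consider a right-censored refit only if the share were large. That is sensible practice within the descriptive analyses already planned, and it would leave the primary result unchanged.
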